## 1.2 Rationale

The purpose of this study is to perform an evaluation of the immunogenicity and safety of the MF59-adjuvanted Quadrivalent cell-based vaccine (aQIVc) versus other influenza vaccines, such as the non-adjuvanted Quadrivalent cell-based influenza vaccine (QIVc), the MF59-adjuvanted Quadrivalent egg-based vaccine (aQIV) and the Quadrivalent recombinant influenza vaccine (QIVr). Immunogenicity and safety will be assessed in the overall study population (adults  $\geq 50$  years of age

and for the age subgroups 50-64 years and  $\geq 65$  years in order to assess the benefit/risk profile in each age population for this vaccine.

### 1.3 Potential Risks and Benefits

Subjects will be exposed to aQIVc or QIVc or aQIV or QIVr vaccines.

As with all injectable vaccines, immediate systemic allergic reactions to vaccination can occur. The reactions for anaphylaxis are sporadic and estimated to be 1.3 per million vaccine doses administered for all vaccines (McNeil 2019). As a precautionary measure, all subjects will remain under observation at the study site for at least 30 minutes after vaccination. Vasovagal syncope (fainting) can occur before or after any vaccination, is usually triggered by the pain or anxiety caused by the injection and is not related to the substance injected. Therefore, it is important that standard precautions and procedures be followed to avoid injury from fainting. Intramuscular vaccination commonly precipitates a transient and self-limiting local inflammatory reaction. This typically includes injection site pain, erythema (redness), or swelling (hardness).

aQIVc is expected to provide benefit over existing conventional influenza vaccines in older adults by both the inclusion of the MF59 adjuvant and the use of antigens produced in cell culture that more closely resemble the wild-type strains (Hedge 2015; Lambert et al. 2010). With the addition of MF59, aQIVc is expected to provide a robust immune response similar to the immune response elicited after vaccination with aQIV in older adults (Frey et al. 2014).

Overall, the clinical safety experience with aQIV and QIVc in older adults, in conjunction with data from the repeat dose aQIVc toxicology study are sufficient to support the initiation of a Phase 2 safety and immunogenicity study in adults 50 years and older. In the repeat-dose toxicity study, three doses of aQIVc, containing [REDACTED] HA/dose, were administered by intramuscular injection to male and female rabbits at 3-week intervals. The vaccine was immunogenic and there was no evidence of local or systemic toxicity. The most common local and systemic reactions observed in the adjuvanted egg-based comparator vaccine (aQIV) in older adults were injection site pain, headache, and fatigue. Most reactions were reported as mild or moderate in intensity. The most common local and systemic reactions associated with administration of the QIVc comparator vaccine in older adults included injection site pain, erythema, induration, headache, fatigue, and myalgia. Most reactions were reported as mild or moderate in intensity. For the aQIVc vaccine, similar local and systemic reactions are to be expected as for the aQIV and QIVc vaccines.

Because the investigational vaccine (aQIVc) has never been administered to humans, additional safety precautions have been incorporated in this study (see [Section 3.8](#), Stopping/Pausing Guidelines).

Please refer to the current Investigator's Brochure (IB) for aQIVc for a summary of potential risks and benefits of aQIVc; to the Product Information for QIVc and QIVr for a summary of potential risks and benefits of QIVc and QIVr respectively, and to the current IB for aQIV for information regarding the potential risks and benefits of aQIV.

## 2 STUDY OBJECTIVES

### 2.1 Primary Objective

#### 2.1.1 Primary Immunogenicity Objective

1. To assess the immunogenicity of aQIVc in comparison with the QIVc, aQIV, and QIVr comparator vaccines as measured by HI assay\* using *cell-derived* target viruses at 28 days after vaccination, in subjects 50-64 and  $\geq 65$  years of age and overall (adults  $\geq 50$  years).

\* *In case of lack of agglutination for a specific strain using HI assay, immunogenicity for that strain will be assessed as measured by microneutralization (MN) assay as an acceptable alternative.*

For primary endpoints, refer to Section 8.1.1, Primary Endpoints.

### 2.2 Secondary Objectives

#### 2.2.1 Secondary Immunogenicity Objective(s)

1. To assess the immunogenicity of aQIVc in comparison with the QIVc, aQIV, and QIVr comparator vaccines as measured by HI assay\* using *cell-derived* target viruses at 180 days after vaccination, in subjects 50-64 and  $\geq 65$  years of age and overall.
2. To assess the immunogenicity of aQIVc in comparison with the QIVc, aQIV, and QIVr comparator vaccines as measured by MN assay using *cell-derived* target viruses at 28 and 180 days after vaccination, in subjects 50-64 and  $\geq 65$  years of age and overall.

\* *In case of lack of agglutination for a specific strain using HI assay, immunogenicity for that strain will be assessed as measured by MN assay as an acceptable alternative.*

For secondary immunogenicity endpoints, refer to [Section 8.1.2.2](#), Secondary Immunogenicity Endpoints.

### 2.2.2 Secondary Safety Objectives

1. To assess the reactogenicity of aQIVc as compared to QIVc, aQIV, and QIVr in subjects 50-64 and  $\geq 65$  years of age and overall for 7 days after vaccination.
2. To assess the safety of study vaccines in subjects 50-64 and  $\geq 65$  years of age and overall for 180 days after vaccination.

For secondary safety endpoints, refer to [Section 8.1.2.1](#), Secondary Safety Endpoints.

### 2.3 Exploratory Objectives

1. The immunogenicity of aQIVc in comparison with the QIVc, aQIV and QIVr comparator vaccines as measured by HI assay may be assessed using *egg-derived* target viruses at 28 days after vaccination, in subjects 50-64 and  $\geq 65$  years of age and overall.
2. Additional exploratory immunogenicity analyses may be conducted to further characterize the immune response of aQIVc.

For exploratory endpoints, refer to [Section 8.1.3](#), Exploratory Endpoints.

[figure not shown]
The results of these exploratory analyses may be presented in an addendum to the Clinical Study Report (CSR).

## 3 STUDY DESIGN

### 3.1 Overview of Study Design

Experimental design: Phase 2, randomized, stratified, controlled, observer-blind, multi-center study in approximately 480 male and female adults aged 50 years and older who are healthy or have comorbidities which increase their risk of complications from influenza infection. An overview of the study design presented in [Figure 3-1](#).

**Figure 3-1: Overview of the Study**

Notes: aDuring this call/visit, non-serious unsolicited adverse events will not be collected. Abbreviations: aQIVc= MF59-adjuvanted Quadrivalent Subunit Inactivated Cell-derived Influenza Vaccine. QIVc= Quadrivalent subunit inactivated cell-derived influenza vaccine. aQIV= MF59-adjuvanted Quadrivalent Subunit Inactivated egg-derived Influenza Vaccine. QIVr= Recombinant Quadrivalent influenza vaccine.

**Duration of the study:** The study duration is approximately 6 months for each subject. The study will be conducted in one single season.

**Vaccination schedule:** Single intramuscular injection on Day 1.

**Investigational Vaccine:** aQIVc.

**Comparator Vaccines:** QIVc, aQIV and QIVr.

**Treatment groups:**

Enrolled subjects will be randomized to one of the four treatment groups in a 1:1:1:1 ratio.

1. aQIVc group: approximately 120 subjects receiving one dose of aQIVc on Day 1.
2. QIVc group: approximately 120 subjects receiving one dose of QIVc on Day 1.
3. aQIV group: approximately 120 subjects receiving one dose of aQIV on Day 1.
4. QIVr group: approximately 120 subjects receiving one dose of QIVr on Day 1.

**Randomization:** an Interactive Response Technology (IRT) will be used in the study with stratification factors for age ( $\geq 50$  to 64 and  $\geq 65$  years, with about 50% of the subjects 50-64 years of

age and about 50% of the subjects  $\geq 65$  years of age for each treatment group) and history of any influenza vaccination within 3 previous influenza seasons (yes/no). Approximately 40% of subjects in each age subgroup for each treatment group should not have been vaccinated with an influenza vaccine within the 3 previous influenza seasons.

Blinding: Observer-blind study.

Blood sample schedule: Three blood samples will be collected from all subjects on Day 1, Day 29 and Day 181.

Data collection: electronic Case Reporting Form (eCRF).

Study periods: The study has a treatment period and a follow-up period. Treatment period (Day 1 to Day 29) and Follow-up Period (Day 30 to Day 181)

Study clinic visits: Three clinic visits for each subject on Day 1, Day 29 and Day 181.

Safety phone call: Two safety phone calls (Day 7 and Day 91) will be conducted to collect any unsolicited Adverse Events (AEs) (on Day 7 only), MAAE, AEs leading to withdrawal, Serious Adverse Events (SAEs) and AESIs, related medications and any vaccinations.

Reactogenicity data collection: Solicited AEs will be recorded daily for 7 consecutive days (or longer if the events are not resolved) following vaccination (Day 1 to Day 7) using a Subject eDiary as completed by the subject.

Safety data collection: Unsolicited AEs will be collected for 28 days after vaccination. SAEs, MAAEs, AEs leading to study withdrawal, and AESIs will be collected during the entire study period. These data will be captured by interviewing the subject during the clinic visits and safety phone calls and by review of available medical records. Subjects will be instructed to call the site in the event of any AE which they perceive as being of concern during the entire study period.

Serological assays:

- HI assay for homologous vaccine strains, using cell-derived target virus, will be performed in all subjects on serum samples collected on Days 1, 29 and 181.
- MN assay for homologous vaccine strains, using cell-derived target virus, will be performed in all subjects on serum samples collected on Days 1, 29 and 181.

### 3.2 Scientific Rationale for Study Design

The design, conduct, and analysis of this study comply with international and regional standards for clinical research in humans, and for investigating the immunogenicity and safety of seasonal influenza virus vaccines.

Since the manufacturing process of aQIVc and QIVc is the same, with the exception of the addition of the MF59 adjuvant in aQIVc, QIVc is chosen as a comparator to assess the adjuvant effect of the addition of MF59 in aQIVc in terms of immunogenicity.

aQIV and QIVr are chosen as comparators to assess the immunogenicity and safety of aQIVc versus 'enhanced' influenza vaccines that are recommended for older adults in some regions.

### 3.3 Justification for Dose

The selected dose and formulation of aQIVc (████ of HA of each viral strain and █████ of MF59 per dose) is expected to be well tolerated and to induce a higher immune response compared to conventional influenza vaccines. █████

████ Safety profiles of aQIV and QIVc have been well characterized in both younger and older adults. No safety concerns were observed from the aQIV and QIVc clinical studies.

### 3.4 Study Period

Each subject should expect to participate in the study for approximately 6 months, from the time of enrolment through the last study visit.

### 3.5 Blinding Procedures

The study is designed as an observer-blind study. Observer-blind means that during the course of the study designated and trained unblinded nurse(s), physician(s), or other qualified health care professional(s) will be responsible for administering the study vaccines to the subjects. They will be instructed not to reveal the identity of the study vaccines either to the subject or to the investigative site personnel (i.e., investigator and study nurse) involved in the conduct of the trial, except in an emergency if unblinding in IRT is not possible. Vaccine administration should be shielded from the subject and blinded study personnel. The unblinded personnel should not be involved in data collection, data entry or data review such as safety assessments and/or collect study data after the vaccinations. Study vaccines will be assigned through an IRT system.

Details of the IRT unblinding procedures will be described in the IRT Manual. If unblinding occurs, either accidental or out of necessity, the Sponsor should be notified promptly.

Investigators, subjects, the Sponsor study team, all laboratory personnel involved in processing samples and performing laboratory assays and others who are directly involved in the conduct of the study or in the analysis of the primary study results, or have contact with study centers, will remain blinded to the treatment codes until the database has been locked for primary analysis.

## 3.6 Data Collection

### 3.6.1 Data Collected from Subjects

The following data will be collected from each subject over the duration of their study participation:

- Demographic Information.
- Medical History, including existing comorbidities.
- Influenza vaccination history.
- Physical examination including temperature, height, and weight.
- Reactogenicity: Solicited AEs for 7 consecutive days (or longer if the events are not resolved) following vaccination (Day 1 through Day 7).
- Unsolicited AEs for 28 days following vaccination (Day 1 through Day 29).
- SAEs, MAAEs, AEs leading to withdrawal from the study, AESIs as collected from Day 1 through Day 181.
- Concomitant Medications/vaccinations (as defined in [Section 6.5](#)).
- Reason for early study termination.

All data collected must only be identified using the Sponsor Subject ID, as described in [Section 5.1.4](#), Randomization.

### 3.6.2 Tools Used for Data Collection

Data will be recorded in the Subject eDiary and collected on Case Report Forms (eCRFs).

#### Subject eDiary

Electronic Diaries (eDiaries), hereafter referred to as Subject eDiaries, will be the only source document allowed for solicited local and systemic adverse events (including body temperature

measurements), starting after the initial 30-minute post-vaccination period at the clinic, and continuing for 7 consecutive days (or longer if the events are not resolved). Refer to the user's manual for further details.

The Investigator or delegated, qualified health care staff should review the Subject's eDiary data and monitor the Subject's eDiary status for compliance on an ongoing basis during eDiary use (Day 1 to Day 7) or longer if events are not resolved.

1. The Subject eDiary will be designed in such a way as to prevent any blank, incomplete or biologically implausible entries during eDiary completion. Subjects will be instructed to fully complete the Subject eDiary each day, as per the instructions provided.
2. Before or just after vaccination, site staff must ensure that each subject's eDiary is prepared for data capture in the ensuing post-vaccination period.
3. Any new safety information reported during the site visit (including a solicited reaction) cannot be entered into the Subject eDiary. Such information must be described in the source notes as a verbally-reported event. Any adverse reaction reported in this fashion must be described as an unsolicited reaction and therefore entered on the adverse event page of the eCRF.

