### Observation Period

After vaccination, the subject will be observed for at least 30 minutes including observation for immediate post-vaccination AE's (unsolicited adverse events). Record all safety data collected during this time in the subject's source document.

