## Other Indicators of Reactogenicity

The use of analgesics/antipyretics will be captured as “absent” or “present” separately by reason “for treatment” or “for prevention”.

The study staff must review the data entered into the Subject eDiary as described in [Section 3.6.2](#), Tools Used for Data Collection and [Section 5.4](#), Post-vaccination Visits.

Note: Any solicited AE that meets any of the following criteria must be entered into subjects’ source document (see [Section 9.1](#), Source Documentation) and also as an AE on the AE eCRF:

- Solicited local or systemic AE that leads to an unscheduled visit to a healthcare provider (MAAE, see [Section 7.1.3](#), Evaluation of Adverse Events).
- Solicited local or systemic AE leading to the subject withdrawing from the study or the subject being withdrawn from the study by the investigator (AE leading to withdrawal, see [Section 7.1.3](#), Evaluation of Adverse Events).
- Solicited local or systemic AE that otherwise meets the definition of a serious AE (see [Section 7.1.4](#), Serious Adverse Events).

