### 7.1.2 Unsolicited Adverse Events

An unsolicited AE is an AE that was not solicited using a Subject eDiary and that was spontaneously communicated by a subject who has signed the informed consent.

Potential unsolicited AEs may be medically attended (defined as symptoms or illnesses requiring hospitalization, or emergency room visit, or visit to/by a health care provider), or were of concern to the subject. In case of such events, subjects will be instructed to contact the site as soon as possible to report the event(s). The detailed information about the reported unsolicited AEs will be collected by the qualified site personnel during the interview and will be documented in the subject’s records.

The period of observation for AEs extends from the time of informed consent until the subject either completes the specified safety follow-up period (Day 181) or at early study termination.

All unsolicited AEs that start during the treatment period (Day 1 to Day 29) will be recorded in the eCRF. During the follow-up (Day 30 to Day 181), unsolicited AEs that meet any reporting criterion (an SAE, AESI, AE leading to withdrawal or a MAAE) are to be recorded in the eCRF.

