7.5 Safety Set

Solicited Safety Set

All subjects in the All Exposed Set with any solicited adverse event data collected on the electronic diary, including temperature measurements or use of analgesics/antipyretics.

Unsolicited Safety Set

All subjects in the All Exposed Set with results of the unsolicited adverse event assessments recorded. A record of safety assessment performed at a specific time point, with confirmation of no AE, is considered as adverse event data hence subject is to be included.

Overall Safety Set

All subjects who are in the Solicited Safety Set or in the Unsolicited Safety Set.

Subjects will be analyzed as "treated" (i.e., according to the vaccine a subject received, rather than the vaccine to which the subject may have been randomized).

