13.3 Unsolicited Adverse Events

This analysis applies to all AE's occurring during the study, judged either as probably related, possibly related, or not related to vaccination by the investigator, recorded in the AE eCRF, with a start date on (but with onset after vaccination) or after the date of vaccination. AE starting prior to study vaccination will only be listed.

The original verbatim terms used by investigators to identify adverse events in the eCRFs will be mapped to preferred terms using the MedDRA dictionary.

The adverse events will then be grouped by MedDRA preferred terms into frequency tables according to system organ class. All reported AEs, as well as AEs judged by the investigator as at

16 MAR 2021 Final Version 2.0

least possibly related to study vaccine, will be summarized according to system organ class and the preferred term within system organ class. These summaries will be presented by the vaccination group. When an AE occurs more than once for a subject, the maximal severity and strongest relationship to the vaccine group will be counted.

The assignment to safety follow-up time intervals will be done by day of onset and not by days ongoing/persisting.

The summaries will be presented by period of onset (Day 1 to Day 29, Day 30 to end of study or Day 1 to end of study). An overview summary will be created by time -period with number and % of subjects with the following categories:

- AE
- AE by maximum severity
- Related (i.e. at least possible) AE
- SAEs
- Related SAEs
- AESIs
- MAAEs
- AEs leading to withdrawal from study
- Deaths.

The following summaries will be produced by SOC and Preferred Term and by time-period (Day 1 to Day 29, Day 30 to end of study or Day 1 to end of study):

- AEs
- AEs by maximum severity
- AEs that are possibly or probably related to the vaccine
- SAEs
- SAEs that are possibly or probably related to the vaccine

- AESIs
- MAAEs
- AEs leading to withdrawal
- Deaths.

Data listings of all adverse events will be provided by subject. In addition, adverse events in the categories above will be provided as listed data.

All tables will be produced overall and by age subgroup.

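### Some solicited reactions are filed as unsolicited, or as both, so eDiary-only reactogenicity rates can be too low and unsolicited AE rates too high

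*Protocol*

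**What the plan says.** **Source of solicited data.** Under Protocol 3.6.2 the eDiary "will be the only source document allowed for solicited local and systemic adverse events", starting once the 30-minute clinic observation is over. The same section adds: "Any new safety information reported during the site visit (including a solicited reaction) cannot be entered into the Subject eDiary". Such a report goes to the AE page: "Any adverse reaction reported in this fashion must be described as an unsolicited reaction". Protocol 5.3 also classes AEs seen in the 30-minute observation as unsolicited. Protocol 7.1, by contrast, names interviews beside diaries as a source of solicited events.

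**Definition and dual entry.** Protocol 7.1.2 states: "An unsolicited AE is an AE that was not solicited using a Subject eDiary". Protocol 7.1.1 (Other Indicators of Reactogenicity) requires certain solicited events to be entered on the AE eCRF as well. The first is a "Solicited local or systemic AE that leads to an unscheduled visit to a healthcare provider"; the others are events leading to withdrawal and serious events.

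**Analysis.** SAP 7.5 limits the Solicited Safety Set to exposed subjects "with any solicited adverse event data collected on the electronic diary". SAP 8.2 treats a wholly empty diary as missing and judges a partly filled one on the days available. The note to SAP Table 3 treats an event as absent when the entry is non-missing and the event is not present. SAP 13.3 takes in every AE "recorded in the AE eCRF, with a start date on (but with onset after vaccination) or after the date of vaccination", with no filter for listed solicited terms. SAP 13.4 provides a combined summary of solicited and unsolicited events, and a separate one for registry posting.

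**The concern.** Protocol 8.1.2.1 has separate secondary endpoints for local and systemic reactions on Days 1-7 and for unsolicited AEs on Days 1-29. The first serves the objective of comparing aQIVc reactogenicity with three vaccines, and aQIVc has not been given to humans before. If the reporting route decides which endpoint a reaction falls under, neither rate measures quite what its label says.

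There are two separate mechanisms. A listed reaction known only from a verbal report, or only from the 30-minute observation, is missing from the solicited tables and present in the unsolicited ones. A diary reaction that also needs an AE page is present in both. Neither document has a step that flags or reverses either case. SAP 13.2 removes subjects without valid data so that rates are not pulled towards zero, yet the first mechanism pulls them the same way.

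**Working it through.** No stated figure in the plan is at issue, so the check follows each type of record through the rules and then bounds the effect.

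**Tracing the records**

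1. *Verbal report at a site visit; diary has some data but none for the event.* Filed as unsolicited (Protocol 3.6.2). The subject stays in the solicited denominator, adds nothing to the numerator for that event, and appears in SAP 13.3.
2. *Same report, no diary data.* The subject is missing from the solicited tables (SAP 8.2, 13.2), not counted as negative, and appears in SAP 13.3.
3. *Same report, another reaction in the diary.* The subject still counts under any solicited AE. Only the specific event is lost.
4. *Event in the 30-minute observation.* Filed as unsolicited. If it persists, the diary opened the same day can still capture it, so only an event that does not reach the diary is lost.
5. *Diary reaction that is medically attended, serious or leads to withdrawal.* Counted as solicited, and again in the SAP 13.3 AE table (and the related-AE table if judged related), against 7.1.2.

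**Weight of one subject.** With 120 per group, 1/120 = 0.83 percentage points. This is the most one subject can add to the unsolicited rate, because a subject with another unsolicited AE is already counted. SAP 13.2 and 13.3 also report by age subgroup. With about half of each group in each stratum (about 60), 1/60 = 1.7 points.

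**Illustration of the first mechanism.** All four inputs are assumptions; the documents give no values.

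- p: true share with a solicited reaction, 30-70%
- f: share of those known only verbally, 2-10%
- c: share of verbal-only subjects with usable diary data showing no event, 0 or 1
- u: true unsolicited AE rate, 10-30%, taken as independent

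Observed solicited rate = (p - pf) / (1 - pf(1 - c)). Rise in the unsolicited rate = (1 - u)pf.

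| p | f | c | Observed solicited rate | Shift (points) |
|---|---|---|---|---|
| 30% | 2% | 1 | 0.294/1 = 29.4% | -0.6 |
| 70% | 10% | 1 | 0.630/1 = 63.0% | -7.0 |
| 30% | 2% | 0 | 0.294/0.994 = 29.6% | -0.4 |
| 50% | 10% | 0 | 0.450/0.950 = 47.4% | -2.6 |

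Over these ranges the solicited rate falls by 0.6 to 7.0 points if every verbal-only subject has a negative diary (c = 1), and by 0.4 to 2.6 points if none has a diary (c = 0). The unsolicited rate rises by between 0.7 x 0.006 = 0.4 points and 0.9 x 0.070 = 6.3 points. The upper ends require 10% of reactors to be verbal-only, which nothing in the documents supports. They are bounds, not estimates.

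**The case against.** A diary completed day by day as the only solicited source is a deliberate choice, and it avoids mixing prompted entries with later recall. It is also protected: the device is designed to prevent blank entries, staff review it throughout its use (Protocol 3.6.2), subjects are phoned after two or more missed days (5.3), and reminders and alerts are issued (5.3.1). Clinic visits fall on Days 1, 29 and 181, and the site-visit wording of 3.6.2 does not expressly cover the Day 7 call, although the 7.1.2 definition points the same way. SAP 8.2 adds complete-diary tables if more than 5% of subjects have incomplete diaries. The analysis is descriptive. All this stands. It argues for few affected subjects and for keeping the diary as the main source. It does not supply a flag, and it leaves the double count untouched.

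SAP 13.4 is a partial answer. Its first summary is general rather than for registry posting, and it recovers the combined total. It does not restore the separate Day 1-7 and Day 1-29 rates.

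A reader might also infer that the comparison between arms is materially distorted. The documents do not show this. In an illustrative upper case with true rates of 50% and 30%, f = 10% and c = 1 in both arms, the observed rates are 45% and 27%. The difference falls from 20 to 18 points, but the ratio stays at 1.67. Whether f differs between arms is unknown.

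Nor do the documents support a claim that pausing decisions would change. Protocol Table 3-1 does set different thresholds for solicited and unsolicited severe events. However, the solicited criteria need Grade 3 on at least two consecutive days, which falls within the daily diary period. The first review is triggered by 7-day data, generally before Day 29 visits, and the IST may pause for any safety concern.

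**Conclusion.** The point holds as a classification fault in reporting. Solicited rates can be too low through verbal-only and observation-period events. Unsolicited and related-AE rates can be too high through those events and through dual entry. The double count follows directly from Protocol 7.1.1 read with SAP 13.3 and needs no assumption about verbal reporting; only its frequency is unknown.

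It would go too far to say that every subject who reports verbally is counted as free of reactions: that requires at least some diary data and no diary entry for the event, and for the any-reaction rate no other diary reaction either. The size is limited to about 0.83 points per subject with 120 per group, and the total cannot be derived from the documents. The primary immunogenicity analysis is unaffected. Because the remedy is cheap and concerns secondary safety endpoints of a new vaccine, it is worth making.

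**What to change.** 1. **Flag.** Mark AE eCRF records that are listed solicited terms with onset on Days 1-7, by a tick box or by programming from preferred term and onset day. Separate those also in the eDiary from those known only verbally or from the 30-minute observation. Review programmed flags blinded, since term and day alone would also catch unrelated headaches or fevers.
2. **SAP 13.3, double count.** Exclude records also in the eDiary from the overall unsolicited and related-AE tables. Keep them in the SAE, MAAE, AESI and withdrawal tables.
3. **SAP 13.3, verbal-only.** Keep these records in the tables, identified as such. Removing them would leave them in neither main endpoint table.
4. **SAP 13.2.** Keep the eDiary as the main source and add one supplementary Day 1-7 table of presence or absence by event, from the eDiary or a flagged AE. Show severity only where the Table 3 grading can be applied: AE-page severity rests on activity limitation (Protocol 7.1.3), whereas erythema, induration and fever are graded by measurement. Say how an unmeasured erythema or induration is handled, as findings under 25 mm are not counted.
5. **Protocol.** Reconcile the mention of interviews in 7.1 with the eDiary-only rule in 3.6.2 and 5.3, and state whether the 3.6.2 rule covers telephone reports.

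The cost is one flag, a short blinded review and one extra table. SAP 13.4 already has solicited events MedDRA-coded, so a programmed flag needs no eCRF change. The downside is some recall error in verbal reports, which is why the added table is supplementary.
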